5.5.8 Study Procedures Post-Vaccine Follow-up

All patients, including those who discontinue protocol therapy early, will be followed for response and toxicity assessments until disease progression, start of a new therapy, or for a maximum of 24 months from study registration (whichever occurs earlier). Follow-up visits should be scheduled per standard-of-care for patients with stable WHO grade II glioma without active treatment (every 3 months). As overall survival is an endpoint of the study, subjects who discontinue protocol therapy must continue to be followed (every 3 months) for survival until death or the conclusion of the study.

For any patient with regimen limiting toxicity (RLT), follow-up will continue as medically appropriate for the specific toxicity until resolution to grade 1 or better or 3 months of no change (stabilization).

If treatment is discontinued for progression, the final study visit will be the final off-study visit, providing there is no ongoing grade 2 or greater treatment related toxicity.

- Physical/neurological examination
- Vital signs
- Interval medical history
- KPS
- Review of concurrent medications
- Adverse event assessment
- MRI scan
- Complete blood count (CBC) with differential and platelet count
- Blood chemistry assessment, including:
 - Alkaline phosphatase, aspartate aminotransferase/alanine aminotransferase (ALT/AST), total bilirubin, calcium, blood urea nitrogen (BUN), creatinine, total protein, albumin, random glucose, potassium, sodium, chloride, bicarbonate.

Serum chemistry and CBC tests are required at the first follow-up visit or when previous tests demonstrated any abnormality. If a patient does not show any abnormality during the course or at the first follow-up visit, that patient will not require CBC and chemistry on the follow-up visits per protocol.

12 April 2020 Page 37 of 88 confidential

5.6 Definition of Regimen Limiting Toxicities (RLT) and Suspension of Enrollment

5.6.1 Definition of RLT

Toxicity will be determined using the revised NCI Common Toxicity Criteria version 5.0 for Toxicity and Adverse Event Reporting (CTCAE) (http://ctep.info.nin.gov).

Management and dose modifications associated with the above adverse events are outlined in Section 5.7.

Participants will be observed for regimen limiting toxicity (RLT) throughout the study. The following are considered to be RLTs if they are judged possibly, probably or definitely associated with treatment. Should they occur, individual participants will be taken off study and no further injections will be given.

- Grade 2 or more any infusion reaction except for Grade 2 pain
- Grade 2 or more cytokine release syndrome
- Grade 2 or more bronchospasm or generalized uticaria (hypersensitivity)
- Grade 2 or more allergic reaction, such as exfoliative erythroderma, anaphylaxis, or vascular collapse
- Grade 2 or more autoimmune disease (e.g. hypothyroidism, autoimmune encephalitis)
- Any Grade 3 or more toxicity possibly, probably, or definitely related to the vaccine or Varlilumab with particular attention to the following events.

The following are also considered RLTs:

- Dosing delays > 6 weeks for IMA950+poly-ICLC vaccines or varillumab (Arm 1 patients only) administration.
- Delay of the scheduled surgical resection for longer than 2 weeks possibly, probably or definitely related to toxicity of the study treatment.

The following are NOT considered RLTs:

- Grade 3 nausea, vomiting, or diarrhea that resolves to ≤ grade 1 with or without treatment within 48 hours
- Grade 3 flu-like symptoms that resolve within 24 hours with the use of acetaminophen 650-1000 mg or with any NSAID

5.6.2 Events Which Will Temporarily Halt Enrollment at Any Time:

Certain events will be considered unacceptable and a single occurrence will lead to temporary closure of enrollment while under review for attribution to study therapy (not related to surgical procedures):

- The occurrence of grade 3 or 4 toxicity, excluding local skin reaction and flu-like symptoms in 3 patients
- Toxicity requiring the use of pressors, including grade 4 vascular leak syndrome or grade 3 and 4 hypotension
- Toxicity requiring ventilation support, including grade 4 respiratory toxicity

12 April 2020 Page 38 of 88 confidential

- Severe brain or brainstem edema leading to grade 4 neurotoxicity and/or requiring significant CNS resuscitation such as Mannitol or artificial ventilation
- Patient death

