- Uncontrolled intercurrent illness including, but not limited to ongoing or active
 infection (e.g. active or chronic hepatitis B and C), symptomatic congestive
 heart failure, unstable angina pectoris, or psychiatric illness/social situations that
 would limit compliance with study requirements

	 History or current status of immune system abnormalities such as hyperimmunity (e.g., autoimmune diseases) that needed to be treated by systemic therapy, such as immuno-suppressants and hypoimmunity (e.g., myelodysplatic disorders, marrow failures, AIDS, transplant immunosuppression). Receiving ongoing treatment with immunosuppressive drugs, or 		
	dexamethasone > 4mg		

Pilot randomized pre-surgical evaluation of varillumab on IMA950 vaccine plus poly-ICLC in patients with WHO grade II low-grade glioma

- 1) Arm 1: Patients will receive IMA950+poly-ICLC and CDX-1127
- 2) Arm 2: Patients will receive IMA950+poly-ICLC.

Drugs included in the current regimen are: 1) IMA950 peptides; 2) poly-ICLC and 3) CDX-1127. IMA950 and poly-ICLC will be administered as one formulation containing 4.96 mg total IMA950 peptides and 1.4 mg poly-ICLC subcutaneously (s.c.) at sub-inguinal sites. CDX-1127 will be administered intravenously (i.v.) at 3 mg/kg

Pre-surgical phase:

On days -23±2, -16±2, -9±2 and -2 relative to the scheduled surgery: All patients receive s.c. injections of IMA950/poly-ICLC vaccine. The 4th dose of pre-surgery IMA950/poly-ICLC vaccine must be administered between 24-48 hrs prior to scheduled surgery. PBMC sample (60-80 mL/draw) is obtained on the day of the 1st vaccine (on day -23±2); also at the D-23±2 visit, PK samples (1 x 10 cc red top tube/draw) will be collected prior to varlilumab administration and 30 minutes (±5 minutes) after the infusion has ended. For Arm 1 patients, Varlilumab (CDX-1127) will be administered i.v. on the day of the first vaccine immediately following the s.c. vaccination.

Surgery: The resected tumor tissue will be sent to the BTRC tumor bank.

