Post-surgery phase: For All patients, at least two weeks after the post-op steroid is tapered, but within 10 weeks post-surgery, the IMA950/poly-ICLC vaccines will be resumed and repeated every 3 weeks for 8 doses (Weeks A1, A4, A7, A10, A13, A16, A19 and A22; defining Week A1 as the week of the first post-surgery vaccine dose). The vaccines will be injected s.c. in the upper fronto-medial side of right thigh with 48±6 hours post-vaccination phone assessment. Patients will be evaluated for any possible adverse events (AEs), regimen limiting toxicity (RLT), and clinical response during clinic visits. For Arm 1 patients, Varlilumab (CDX-1127) will be administered i.v. on the day of A1, A7, A13 and A19 vaccines following the s.c. vaccination and PK samples (1 x10 cc red top tube/draw) will be collected prior to varlilumab administration and 30 minutes (+ 5 minutes) after the infusion has ended .

Weeks A1, A13, A19 and A25: PBMC samples (80 mL/draw) will be obtained to monitor induction of anti-IMA950 T-cell responses as well as T-cell and myeloid cell subsets by flow-cytometry.

Post-Op (within 4 weeks before Week A1) Weeks A10 and A25: MRI scans

12 April 2020 Page 11 of 88 confidential

Study Objectives:

Primary (two co-primary endpoints):

Safety: We will evaluate the incidence and severity of adverse events associated with the treatment regime, with an early stopping rule based on the frequency of Regimen Limiting Toxicity (RLT).

Immunological activity. We will determine the magnitude of CD4+ and CD8+ T-cell responses against the IMA950 peptides in pre- and post-vaccine PBMC using a novel, flow-cytometry-based 2D *ex vivo* assay system. We will determine whether Arm 1 patients demonstrate significantly higher magnitude of response compared with Arm 2 patients.

Exploratory

- 1. To evaluate IMA950-reactive T-cell infiltration and CXCL9/10 expression in tumors resected from Arm 1 and Arm 2 patients (We will compare these readouts between the two groups in a preliminary manner and the historical control patients who were enrolled in IRB# 15-17078 vaccine study).
- 2. To evaluate IMA950-reactive T-cell receptor (TCR) clonotypes in tumors resected from Arm 1 and Arm 2 patients (We will compare this between the two groups in a preliminary manner (and the historical control patients who were enrolled in IRB# 15-17078 vaccine study).

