- (Arm 1 patients only) on the day of Varlilumab infusion (Weeks A7, A13 and A19), PK samples (1 x 10 cc red top tube/draw) should be drawn from the arm contralateral to the infusion site prior to administration and at 30

minutes (±5 minutes) after the end of the varlilumab infusion. An additional sample should be drawn as soon as possible for any patients who experience an infusion reaction.

- MRI scan on Weeks A10
- Assessment of vaccine injection site 48±6 hours post-injection which can be done either by phone or in person

5.5.6Study Procedures Week A25

These procedures must be completed ± 7 days

- Physical/neurological examination
- Vital signs
- Interval medical history
- KPS
- Review of concurrent medications
- Adverse event assessment
- Complete blood count (CBC) with differential and platelet count
- Blood chemistry assessment, including:
- Alkaline phosphatase, aspartate aminotransferase/alanine aminotransferase (ALT/AST), total bilirubin, calcium, blood urea nitrogen (BUN), creatinine, total protein, albumin, random glucose, potassium, sodium, chloride, bicarbonate
- Collection of 8 x 10cc green top tubes and 1 x 5cc red top tubes for research blood samples
- MRI scan
- ECG (if clinically indicated)

5.5.7 48 Hour Post-Vaccine Follow-up

Skin reactions secondary to the vaccine administration may lead to unique skin toxicity. Furthermore, the regime may cause systemic adverse events. Hence, observations for severe local and systemic reactions will be important. Patients will have follow-up at 48 ± 6 hours after each vaccine for adverse events. This may be by telephone assessment or in person.

If 48 ± 6 hours post-vaccine assessment is by telephone, the patient/parent/guardian will use the Vaccination Toxicity Assessment Form (Appendix III) to permit an accurate and consistent assessment of vaccine site reactions. Any telephone reported reactions consistent with ≥ Grade 3 should be followed by a clinic visit and appropriate management. Such a visit would ideally be with the primary research team and accomplished within 24-72 hours; however, if the patient is unable to travel to UCSF, then appropriate local referral will be facilitated (e.g., Dermatology, etc.).

12 April 2020 Page 36 of 88 confidential

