12.2 Stopping Rule for Toxicity

The trial will be stopped for toxicity if the number of patients experiencing RLT in either arm is excessive. A probability of RLT (pRLT) exceeding 0.33 would be considered prohibitively high. Based on the previous experience in UPCI 07-057 and UPCI 08-135, we believe the expected pRLT is 1/20, and that the probability pRLT is equal to or greater than 0.33 is 0.05. We will use a continuous Bayesian beta-binomial monitoring rule: stop the trial if the estimated P(RLT>0.33)>0.33. We will use a beta prior distribution with

12 April 2020 Page 76 of 88 confidential

[figure not shown]
parameters α =0.09 and β =1.71, representing our beliefs above. The stopping rule is specified in the table.

# Patients	# RLT	# Patients	# RLT	
3	2	12	4	
4	2	13	5	
5	2	14	5	
6	3	15	5	
7	3			
8	3			
9	3			
10	4			
11	4			

Stopping rule for toxicity: for the given number of patients in the either arm, the trial is halted if the number of RLTs equals the given number

[figure not shown]
The operating characteristics of this rule were determined by Monte Carlo simulation and are displayed in the graph. It is seen that if the true pRLT>0.33, the expected number of patients enrolled is five and the probability the trial stops early is 0.75, but if the true pRLT=0.1, the probability the trial stops early equals 0.2.

12 April 2020 Page 77 of 88 confidential

Operating characteristics of the stopping rule. The blue line is the expected number of patients in the trial (left axis) and the red line is the probability the trial stops early (right axis) as a function of the true (unobserved) pRLT.

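### The 12.2 toxicity rule defines neither an RLT window nor its patient count, and its stated 0.75 chance of stopping is reproduced only if every RLT outcome is known at once

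*Combined protocol and SAP*

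**What the plan says.** Section 5.6.1 sets no time limit on RLTs: "Participants will be observed for regimen limiting toxicity (RLT) throughout the study". The Protocol Synopsis starts vaccination before surgery ("On days -23±2, -16±2, -9±2 and -2 relative to the scheduled surgery") and restarts it afterwards: "within 10 weeks post-surgery, the IMA950/poly-ICLC vaccines will be resumed and repeated every 3 weeks for 8 doses". Section 5.5.6 places the last treatment-period visit at Week A25. Under section 5.5.8 patients are then "followed for response and toxicity assessments until disease progression, start of a new therapy, or for a maximum of 24 months". Four of the five varlilumab infusions (A1, A7, A13, A19) come after surgery.

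Section 12.2 stops the trial when the posterior probability that the RLT rate exceeds 0.33 is itself above 0.33, under a beta prior with "parameters α =0.09 and β =1.71, representing our beliefs above". The resulting table is applied "for the given number of patients in the either arm". For a true rate above 0.33, the section reports that "the expected number of patients enrolled is five and the probability the trial stops early is 0.75". It does not say whether a counted patient is enrolled, treated or fully observed.

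The lead-in in section 4.1 makes each early patient wait until the previous one is at least 6 weeks past surgery. Once both arms are found tolerable, patients are randomised with no such wait.

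**The concern.** A beta-binomial rule treats each counted patient as a known success or failure. If the table is entered with patients enrolled, someone who started yesterday counts as a full RLT-free patient. RLTs that appear later then meet a denominator that has already grown, so the boundary is harder to reach.

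The documents make late RLTs plausible. In the earlier low-grade glioma vaccine study, the one RLT followed the 7th vaccine (5.8.2). Section 5.8.5 expects immune-related events several weeks to a few months after treatment starts. Safety is a co-primary endpoint and this is the trial's formal early stopping rule, so its stated properties should describe the trial as it will run.

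**Working it through.** **Inputs.** Prior Beta(0.09, 1.71), threshold 0.33 and the table boundaries are from 12.2. The 15 patients per arm are from 12.1.2. Accrual of 1-2 a month in total (Synopsis) gives 0.5-1 per arm per month.

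- Treatment course: 23 days (3.3 weeks) + up to 10 weeks + 24 weeks (A1 to A25) = 37.3 weeks at most, or about 8.6 months.
- Lead-in gap: 3.3 + 6 = 9.3 weeks.
- Patients within their course at the same time: 8.6 × 0.5 to 8.6 × 1, about 4 to 9 per arm.

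**The plan's own figures.** With x RLTs in n patients, stop if P(p > 0.33) > 0.33 under Beta(0.09 + x, 1.71 + n − x). The prior mean is 0.09/1.80 = 0.05 and its tail above 0.33 is 0.050, as stated. The formula gives the printed boundary at every n from 3 to 15. An exact forward recursion at a true rate of 0.33, with each outcome known before the next patient is counted, gives a 0.759 chance of stopping (0.740 before the 15th patient) and a mean of 7.8 enrolled. That matches the stated 0.75, per arm.

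**How dilution works.** Three RLTs in 9 patients give a tail of 0.345, so the arm stops. Three in 10 give 0.273, so it continues, even if the tenth patient has just started.

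**Delayed outcomes, n = patients enrolled.** One arm was simulated at a true rate of 0.33 with the 9.3-week gaps at the start. The table was checked at each enrolment and each RLT (simulation error about 0.01). Ranges cover 0.5 to 1 patient per arm per month.

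| RLT timing (assumed) | Ever stops | Stops before 15 enrolled | Mean enrolled |
|---|---|---|---|
| Known at once | 0.76 | 0.74 | 7.8 |
| All in first 9.3 weeks | 0.72-0.73 | 0.67-0.70 | 8.4-8.7 |
| Uniform over 37.3 weeks | 0.63-0.68 | 0.41-0.58 | 10.1-11.7 |
| All after surgery | 0.61-0.67 | 0.28-0.52 | 11.0-13.1 |

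Adding the section 4.1 lead-in closure (2 or more RLTs among up to 6 patients) changes the uniform row little: 0.65-0.69 ever and 0.45-0.60 before full.

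**Follow-up weighting.** Replace n − x by the sum, over RLT-free patients, of the fraction of the window completed.

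- *No floor.* One RLT stops the arm whenever the RLT-free weight is about 1.29 or less. When the third lead-in patient enters, the first two carry 18.6/37.3 + 9.3/37.3 = 0.75. A single RLT in that patient then gives P(p > 0.33) = 0.41 under Beta(1.09, 2.46), and the arm would stop. Section 4.1 instead enrols three more patients. Stopping at a true rate of 0.10 is about 0.20-0.22 (uniform) and about 0.3 (early).
- *Floor of 3 patients and 2 RLTs, as in the table.* With uniform timing at 0.33, ever stopping is about 0.75 and stopping before full about 0.65-0.70. At 0.10, stopping is about 0.10-0.11, against 0.106 with outcomes known at once. With early RLTs, stopping at 0.10 is about 0.15-0.20.

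**The case against.** **The denominator is undefined, not shown to be wrong.** A reader might infer that the rule stops a toxic arm less often than stated, full stop. The documents do not support that, because 12.2 never says that n means patients enrolled. If only patients with a completed outcome counted, ever stopping at 0.33 under uniform timing would be 0.84-0.88, above the stated figure, and 0.17-0.22 at a true rate of 0.10. This stands. It changes the point to an unspecified rule, since under both readings the stated properties do not hold.

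**RLTs may come early.** The 5.6.1 list includes infusion reactions, cytokine release, hypersensitivity and delay of surgery. If all RLTs fell in the first 9 weeks, the loss would be only a few points. This also stands, so the full range is given and no single figure should be quoted.

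**Full accrual is not the end of the rule.** Monitoring is continuous, so a later crossing still halts the trial. Hence both measures are shown; the loss in ever stopping is much the smaller.

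**Other safeguards exist.** A reader might also infer that a toxic arm would enrol unchecked. Section 5.6.2 temporarily halts enrolment after grade 3 or 4 toxicity in 3 patients (with exclusions), or after one death or one event needing pressors or ventilation. Section 4.1 closes an arm at two lead-in RLTs, and section 11 adds weekly toxicity review. These are real partial protections. The 5.6.2 halts are temporary and their grade 3-4 count omits grade 2 RLTs. None of them restores the 0.75 claimed for the 12.2 rule.

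**Conclusion.** The point holds as a gap in specification with a measurable consequence. The 0.75 describes a trial in which each RLT outcome is known at once, which a course of up to 37 weeks and unstaggered randomisation do not provide. With n read as patients enrolled, the chance of ever stopping at a true rate of 0.33 is about 0.63-0.68 (uniform timing) or 0.72-0.73 (early). Before the arm is full it is about 0.41-0.58 or 0.67-0.70. The direction is the same under every accrual rate and timing tried on that reading. The size rests on assumed RLT timing, the longest allowed gap after surgery and the planned accrual.

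The other stated figures also need a common basis. The 0.2 at a true rate of 0.10 fits either of two arms stopping, 1 − (1 − 0.106)² = 0.20, whereas 0.75 at 0.33 fits one arm. The expected five patients is not the per-arm mean of 7.8. This should be corrected, but it is not evidence that participants lack other protection.

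**What to change.** In section 12.2:

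1. State the window over which RLTs count for the rule. The treatment course of up to 37 weeks and the follow-up of up to 24 months are both possible on the present text; the figures here use the former. State also which patients enter the denominator.
2. Enter the rule with follow-up-weighted patients: 1 for a patient with an RLT, and the fraction of the window completed for a patient without. Keep Beta(0.09, 1.71) and the 0.33 threshold.
3. Keep the table's minimum of 3 patients and 2 RLTs, so that the rule does not override the lead-in in 4.1.
4. Restate stopping probabilities and expected enrolment under planned accrual for early, uniform and late RLTs, saying whether each is per arm or for either arm.

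The cost is SAP wording, one simulation and a short calculation at each review in place of a table lookup. No dose, schedule or RLT definition changes. The downside is more false stopping if RLTs come early: about 0.15-0.20 at a true rate of 0.10. If the sponsor prefers a table entered with patients enrolled, say so and replace the 0.75 with the lower range.

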5.7.3 Discontinuation of the regimen

Vaccine administration will be discontinued in the following situations:

- o An RLT is observed
- o If there is a delay of scheduled craniotomy greater than 2 weeks
- If there is a delay of vaccine dosing greater than 6 weeks due to treatment related toxicity or regimen-limiting toxicity (RLT)

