5.8.4 Management of Infusion Reactions to Varlilumab

Varlilumab contains only human immunoglobulin protein sequences and is unlikely to be immunogenic. Infusion or hypersensitivity reactions are expected to be infrequent events. However, if such a reaction were to occur, it might manifest with fever, chills, rigors, headache, rash, pruritus, arthralgias, hypo- or hypertension, bronchospasm, or other symptoms. All grade 3 or 4 infusion reactions should be reported within 24 hours to the Celldex Medical Monitor and reported as an SAE. Infusion reactions should be graded according to NCI CTCAE (version 5.0) guidelines. Treatment guidelines are provided below.

For grade 1 symptoms: (Mild reaction; infusion interruption not indicated; intervention not indicated)

Remain at bedside and monitor subject until recovery from symptoms. The following prophylactic premedications are recommended for future infusions: diphenhydramine 50 mg (or equivalent) and/or paracetamol 325 to 1000 mg (acetaminophen) at least 30 minutes before additional varillumab administrations.

For grade 2 symptoms: (Moderate reaction requires therapy or infusion interruption but responds promptly to symptomatic treatment [e.g., antihistamines, non-steroidal anti-inflammatory drugs, narcotics, corticosteroids, bronchodilators, IV fluids]; prophylactic medications indicated for 24 hours).

Stop the varlilumab infusion, begin an IV infusion of normal saline, and treat the subject with diphenhydramine 50 mg IV (or equivalent) and/or paracetamol 325 to 1000 mg (acetaminophen); remain at bedside and monitor subject until resolution of symptoms. Corticosteroid or bronchodilator therapy may also be administered as appropriate. If the infusion is interrupted, then restart the infusion at 50% of the original infusion rate when symptoms resolve; if no further complications ensue after 30 minutes, the rate may be

12 April 2020 Page 49 of 88 confidential

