increased to 100% of the original infusion rate. Monitor subject closely. If symptoms recur then no further varillumab will be administered at that visit. Administer diphenhydramine 50 mg IV, and remain at bedside and monitor the subject until resolution of symptoms. The amount of study drug infused must be recorded on the electronic case report form (eCRF). The following prophylactic premedications are recommended for future infusions: diphenhydramine 50 mg (or equivalent) and/or paracetamol 325 to 1000 mg (acetaminophen) should be administered at least 30 minutes before additional varillumab administrations. If necessary, corticosteroids (recommended dose: up to 25 mg of IV hydrocortisone or equivalent) may be used.

For grade 3 or grade 4 symptoms: (Severe reaction, grade 3: prolonged [i.e., not rapidly responsive to symptomatic medication and/or brief interruption of infusion]; recurrence of symptoms following initial improvement; hospitalization indicated for other clinical sequelae [e.g., renal impairment, pulmonary infiltrates]. Grade 4: life threatening; pressor or ventilatory support indicated.)

Immediately discontinue infusion of varlilumab. Begin an IV infusion of normal saline, and treat the subject as follows. Recommend bronchodilators, epinephrine 0.2 to 1 mg of a 1:1,000 solution for subcutaneous administration or 0.1 to 0.25 mg of a 1:10,000 solution injected slowly for IV administration, and/or diphenhydramine 50 mg IV with methylprednisolone 100 mg IV (or equivalent), as needed. Subject should be monitored until the investigator is comfortable that the symptoms will not recur. Varlilumab will be permanently discontinued. Investigators should follow their institutional guidelines for the treatment of anaphylaxis. Remain at bedside and monitor subject until recovery from symptoms. In the case of late-occurring hypersensitivity symptoms (e.g., appearance of a localized or generalized pruritus within 1 week after treatment), symptomatic treatment may be given (e.g., oral antihistamine, or corticosteroids).

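### After a related Grade 2 varlilumab infusion reaction other than pain, 5.6.1 takes the patient off study, while 5.8.4 restarts the infusion and plans for further doses

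*Combined protocol and SAP*

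**What the plan says.** **Stopping.** Section 5.6.1 lists as an RLT, if at least possibly related to treatment, "Grade 2 or more any infusion reaction except for Grade 2 pain". A separate item lists "Grade 2 or more bronchospasm or generalized uticaria (hypersensitivity"). The consequence is that "individual participants will be taken off study and no further injections will be given". Section 5.6.1 also says that "Management and dose modifications associated with the above adverse events are outlined in Section 5.7". Within 5.7, section 5.7.3 discontinues vaccination when "An RLT is observed". Section 5.10 likewise ends treatment at a limiting toxicity as already defined.

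**Continuing.** Section 5.8.4 defines a Grade 2 reaction as a moderate one that needs treatment or interruption and responds promptly. Staff stop the infusion, start saline, and give diphenhydramine and/or acetaminophen. "Corticosteroid or bronchodilator therapy may also be administered as appropriate". If the infusion was interrupted, they "restart the infusion at 50% of the original infusion rate" once symptoms resolve, and may return to the full rate after 30 uneventful minutes. For later visits, premedication "should be administered at least 30 minutes before additional varillumab administrations". Permanent discontinuation of varlilumab appears only under Grade 3 or 4.

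**The concern.** The two instructions cannot both be carried out: a patient who is off study has no later infusions to be premedicated for. The section that infusion staff would naturally open during a reaction is the one on managing varlilumab infusion reactions, and it sends them back to dosing without saying that an RLT may just have occurred. At stake is the re-exposure of an Arm 1 patient to an antibody after an event that the protocol treats as limiting.

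**Working it through.** The check is a comparison of text, followed by a count of the infusions at issue. The plan states no figure of its own on this point.

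**Step 1. The event.** Take an Arm 1 patient with a Grade 2 reaction to varlilumab, not pain, at least possibly related, which resolves with treatment and does not recur.

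**Step 2. The instructions side by side.**

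| Question | 5.6.1, 5.7.3, 5.10 | 5.8.4, Grade 2 paragraph |
|---|---|---|
| Is it an RLT? | Yes | Not mentioned |
| Today's infusion | Ends; patient off study | Restart at half rate, then full rate |
| Later varlilumab | None | Continues, with premedication recommended |
| Vaccine | Stops | Not mentioned |

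The first row is silence. The second and third rows are direct conflicts. The fourth is not, because 5.8.4 says nothing about the vaccine.

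**Step 3. Can the texts be reconciled?**
- *5.8.4 might cover only the Grade 2 pain exception.* It is not written that way. It names fever, rigors, rash, blood pressure changes and bronchospasm as manifestations, and its Grade 2 paragraph allows bronchodilators. Bronchospasm of Grade 2 or more is an RLT in its own right.
- *The bar on injections might mean vaccine only.* Removal from the study still leaves no later infusions.
- *The reaction might be unrelated.* Then it is not an RLT and there is no conflict. But the threshold is only possible relatedness, which a reaction to the infusion would normally meet.

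**Step 4. Where the conflict is clean.** Grade 2 pain and unrelated reactions fall outside it. Recurrence is less clear: the Grade 2 paragraph then withholds varlilumab only for that visit, whereas the Grade 3 description includes recurrence after improvement and leads to permanent discontinuation. The clear case is the reaction that resolves and does not recur.

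**Step 5. Size of the re-exposure.** Arm 1 has 5 infusions: day -23, A1, A7, A13 and A19 (section 6 calendar; section 7.3). After a reaction at infusion k, 5 − k remain:

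| Reaction at | Day -23 | A1 | A7 | A13 | A19 |
|---|---|---|---|---|---|
| Infusions left under 5.6.1 | 0 | 0 | 0 | 0 | 0 |
| Infusions left under 5.8.4, at most | 4 | 3 | 2 | 1 | 0 |

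In every column 5.8.4 also allows the rest of the interrupted infusion.

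**The case against.** **Precedence leans one way.** Section 5.6.1 is mandatory and refers management to 5.7, and 5.7.3 and 5.10 agree with it. Section 5.8.4 calls itself treatment guidelines, sits among the expected risks, and words later premedication as a recommendation. This stands in part: a careful reader would probably conclude that the patient must stop. But no text says that 5.6.1 overrides 5.8.4, and the restart sentence is an instruction.

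**Stronger readings.** A reader might infer three further consequences. The documents do not establish them.

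- *Continued vaccination.* After a day -23 reaction, 12 − 1 = 11 vaccines remain of 4 pre-surgery plus 8 post-surgery. Section 5.8.4 does not say that they may be given. It covers varlilumab only, so the vaccine stop in 5.6.1 and 5.7.3 is not expressly contradicted.
- *Evaluability.* Section 4.3 requires at least four post-surgery vaccines for the immunological endpoint. Removal at day -23, A1, A7, A13 or A19 leaves 0, 1, 3, 5 or 7. The first three fall short, so such a patient would be replaced. That 5.8.4 would instead keep the patient evaluable rests on the same unstated continuation of vaccine.
- *RLT counts.* With the section 12.2 prior, r RLTs in 3 patients give a Beta(0.09 + r, 1.71 + 3 − r) posterior. For r = 2, Beta(2.09, 2.71) gives P(pRLT > 0.33) = 0.661; for r = 1, Beta(1.09, 3.71) gives 0.252. The stopping limit of 0.33 lies between them. In section 4.1 the same change turns an intolerable Arm 1 into one that adds three patients. This requires two RLTs among three patients, with one unrecorded. Section 5.8.4 does not redefine an RLT, so the counts for 4.1, 12.1.1 and 12.2 should be the same whichever management text is followed. Adverse event recording (10.2), weekly Site Committee review and Data and Safety Monitoring Committee oversight (11.1) also guard against a missed event.

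**Conclusion.** The inconsistency is real and lies in patient management, not in how an RLT is defined. For a related Grade 2 varlilumab reaction other than pain, one set of sections removes the patient and another resumes the drug. The established size is the remainder of the interrupted infusion plus up to 4 further infusions, the maximum applying to a reaction on day -23. This assumes that staff follow 5.8.4 as written and that the investigator judges the reaction at least possibly related.

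How often it would arise cannot be stated: the text available gives no rate of Grade 2 infusion reactions, and 5.8.4 expects infusion reactions to be infrequent. The possible effects on vaccination, evaluability and RLT counts are reasons to tidy the text. They are not demonstrated faults in the lead-in, the stopping rule or the between-arm comparisons.

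**What to change.** Let 5.6.1 govern and edit only the Grade 2 paragraph of 5.8.4.

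1. Keep the acute care there: stop the infusion, saline, diphenhydramine, acetaminophen, corticosteroid or bronchodilator as needed, and bedside monitoring. It must stay in this paragraph, because the Grade 1 text above it calls for no intervention.
2. Add: *If the reaction is other than Grade 2 pain and is judged at least possibly related to treatment, it is an RLT under 5.6.1: do not restart the infusion, give no further varlilumab or vaccine, and record the RLT.*
3. Limit the restart and future-premedication text to Grade 2 pain or reactions judged unrelated.

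The Grade 1 and Grade 3–4 text need not change. The cost is one paragraph. The downside is that patients with a promptly reversible related Grade 2 reaction lose further treatment, but 5.6.1 already requires that. The sponsor could instead narrow the RLT, for example to Grade 3 or higher, or to Grade 2 reactions that recur or do not resolve promptly. That would relax a safety criterion and change the event counted in the lead-in, the stopping rule and the Fisher test, so it is the larger amendment.
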